1.2. Methadone providers

Methadone providers will conduct the study interventions under the clinical supervision of the study master counselors. All methadone providers have been trained on basic addiction medicine and will receive further training to deliver the study interventions. We will conduct in-depth interviews with them before and after the intervention phase.

Randomization and Interventions

An investigator will stratify participants by HIV status and randomize them into two frontline interventions using REDCap, as shown in Figure 1. She will send the allocation results to the site research assistants who will then inform providers at the study clinics. This is an open label study so unblinding does not occur. Participants and their counselors, research assistants and data managers are aware of participants' assignment of intervention. Participants will receive two individual sessions of motivational interviewing with their counselors before they get into the frontline interventions and, in Week 13, before the adaptive strategies start. These sessions would boost participants' motivation for intervention and provide them with greater details of the upcoming intervention activities.

Two frontline interventions (Weeks 1-12)

- High intensity: Participants in this arm receive contingency management with the escalating-and-reset schedule throughout 12 weeks. This schedule means participants receive increasing rewards for consecutive negative UDS but if the streak of negative UDS is broken,

their rewards return to the starting level. The maximal reward value over 12 weeks is \$150 USD, equivalent to the average monthly income of our participants.

- Low intensity: Participants in this arm receive contingency management for the first six weeks with the maximal reward value of \$40 USD. For the last six weeks, they attend weekly group education sessions. The topics of group education include 1) Addiction mechanism, 2) Road to recovery, 3) Coping with triggers, 4) Boredom, 5) Building trust and 6) Relapse prevention.

Participants with four consecutive UDS negative with methamphetamine in weeks 11 and 12 are considered to be responsive to frontline interventions. Others are considered non-responsive. Responders to frontline interventions are placed in the maintenance treatment arm. Non-responders are randomized to either enhanced treatment 1 or 2.

Three adaptive strategies (Weeks 14-25)

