- Maintenance treatment: Participants receive two daily automatic unidirectional scripted SMS reminders plus one weekly self-monitoring assessment message over 12 weeks.
- Enhanced treatment 1: Participants attend 12 weekly Matrix group counseling sessions facilitated by the clinic counselors. Our Matrix intervention has the same structure, albeit it is shorter than the original 24-sessions model.
- Enhanced treatment 2: Participants receive the same Matrix intervention plus contingency management over 12 weeks.

Definition of effectiveness measures

Effectiveness measures will be assessed at 13-, 26- and 49 weeks after the first week of frontline interventions and throughout the interventions. Primary outcomes include: (1) increase in HIV viral suppression for HIV-positive participants at 26- and 49-weeks; (2) reduction in HIV risk behaviors for both HIV-positive and HIV-negative participants at 26- and 49-weeks; and (3) reduction in methamphetamine use at 13-, 26- and 49-weeks measured by UDS (point abstinence) and self-report (continuous abstinence and longest period). Secondary outcomes include: (1) adherence to antiretroviral treatment for HIV-positive participants; 2) frequency of HIV testing for HIV-negative participants; 3) heroin use with UDS; 4) opioid overdose; and, 5) quality of life.

To acquire the primary and secondary outcomes, we will assess for the following:

- HIV viral load test. At baseline, Week 13, Week 26 and Week 49, we send blood samples of HIV-positive participants to laboratories at Bach Mai Hospital in Hanoi and HCMC University of Medicine and Pharmacy Hospital in HCMC for viral load quantification.

- Drug screening. We use an FDA-approved Multi-Drug Rapid Test Panel to detect methamphetamine, opioid, and cannabis in urine twice a week throughout the intervention period and at Week 49.
- Methadone and HIV treatment. We extract methadone and HIV treatment data from participants' medical charts. Variables of interest include length of treatment, treatment regimen, medication dose and treatment adherence.

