Barriers to access to care	X		X	X
BACE				
Mental health	X		X	X
Depression, Anxiety, Stress Scale (DASS-21)				
Social support	X		X	X
(MOS-SS)				
Quality of life	X			X
(EQ-5D-5L)				
Stigmatisation	X			X
Towards people who are under methadone treatment				
(MMT-SMS)				
Toward people who use drugs				
Toward people living with HIV				
Treatment information (from medical charts)	X	X	X	X
Methadone maintenance treatment				
HIV treatment				
Cost data	X		X	X
Opportunity costs				
Other healthcare costs				
Social costs				
Tests				
Quick and confirmatory HIV tests (not for participants with known HIV seropositivity)	X	X	X	X
Viral load test	X	X	X	X
UDS	Twice a week throughout intervention			X
Ethnographic observation	X	X	X	X
Qualitative interviews	X		X	

Data management

Different datasets collected from different sources will be linked through a unique identification code using REDCap (Research Electronic Data Capture) for quantitative data. Data will be uploaded in real-time from the 20 study clinics onto our database. The study data manager will assess transferred data for completeness, query sites regarding any inconsistencies, and code merged data files for analysis.

For qualitative data, field notes written on site are expanded and recorded electronically within 24 hours. After removing all personal identifiable information, the research team will upload password-protected transcripts on a secured database. The transcripts will be uploaded into Atlas.ti software to organize data and facilitate analysis.

Data analysis

To assess effectiveness

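### UDS point abstinence is primary at weeks 13 and 26, but no week 26 urine is scheduled, week 13 is unclear, and the plan does not say which urine supplies either value

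*Combined protocol and SAP*

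**What the plan says.** The section Definition of effectiveness measures gives as the third primary outcome "reduction in methamphetamine use at 13-, 26- and 49-weeks measured by UDS (point abstinence) and self-report (continuous abstinence and longest period". The drug screening bullet in the same section says the panel is used to "detect methamphetamine, opioid, and cannabis in urine twice a week throughout the intervention period and at Week 49". The UDS row of Table 1 agrees: it reads "Twice a week throughout intervention" and then has an X under Week 49.

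The viral load bullet is fuller: "At baseline, Week 13, Week 26 and Week 49, we send blood samples of HIV-positive participants".

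Randomization and Interventions sets the stages: "Two frontline interventions (Weeks 1-12") and "Three adaptive strategies (Weeks 14-25"). Week 13 lies between them and holds the motivational interviewing that precedes the adaptive strategies. Rewards for negative urines run through week 12 in the high-intensity arm. In the low-intensity arm, "Participants in this arm receive contingency management for the first six weeks", followed by group education. In the second stage, enhanced treatment 1 is Matrix alone and enhanced treatment 2 is Matrix plus contingency management for 12 weeks. Response is defined by four consecutive negative urines in weeks 11 and 12.

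**The concern.** A site that follows the schedule exactly will have no urine in week 26, and will have one in week 13 only if it counts that week as part of the intervention period. The analyst must then obtain the two primary values some other way, and the plan does not say how. The options include an unlisted visit urine, the last treatment-phase urine, and treating the value as missing.

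These options do not measure the same thing. A week 12 urine is collected while one frontline arm is paid for a negative result and the other is not. A week 25 urine is collected while one enhanced arm is paid and the other is not. A live payment can affect attendance and the timing of use, as well as underlying use. The trial is open label, and the clinic nurse both collects the urine and runs the rewards. The week 12 urines also feed the response rule, so using one as the week 13 outcome would largely repeat the variable that sends participants to their second-stage treatment. At stake is what the week 13 and week 26 UDS results mean, and whether two analysts would obtain the same ones.

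**Working it through.** **1. Schedule against outcome.**

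| Time point | Primary UDS outcome? | Urine scheduled? | Nearest scheduled treatment-phase urine | Rewarded in |
|---|---|---|---|---|
| Week 13 | Yes | Unclear (between stages) | Week 12 | High intensity only |
| Week 26 | Yes | No (stage 2 ends in week 25) | Week 25 | Enhanced treatment 2 only |
| Week 49 | Yes | Yes, named | Not needed | No arm |

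The visit clock adds doubt. The outcome section counts weeks after the first week of frontline treatment. Read literally, 13, 26 and 49 become calendar weeks 14, 27 and 50, whereas Table 1 uses Week 13, Week 26 and Week 49. Week 14 falls inside stage 2, where urine is taken twice weekly. Week 27 is still outside it, so the second gap remains on either reading.

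Table 1 as extracted also has no Week 13 mark for current drug use, so the self-report half of the week 13 outcome appears to lack a scheduled assessment too.

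**2. The plan's own figure.** Sample size determination gives 100 HIV-positive participants per group, 80% power, 5% alpha (two-sided assumed), 20% attrition and a detectable difference of 20 points. Evaluable per group: 100 × 0.8 = 80. With p̄ the mean of p1 and p2:

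power = Φ{ [ |p1 − p2|√n − 1.96√(2p̄(1 − p̄)) ] / √[p1(1 − p1) + p2(1 − p2)] }

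- 80% v 60%: (1.789 − 1.270)/0.632 = 0.820, power 79.4%.
- 90% v 70%: (1.789 − 1.109)/0.548 = 1.242, power 89.3%.

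The figure reproduces and is not in dispute. The 20 points apply to the 200 HIV-positive participants; the section says that smaller differences in substance use are detectable in the larger samples.

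**3. Illustration of the stake (gaps assumed).** Suppose the reward alone produced a gap in the last treatment-phase urine that would be absent in an unrewarded urine. Take the plan's 80-90% base rate for substance use as UDS positivity, with 20% attrition. Evaluable per arm: stage 1, 600 × 0.8/2 = 240; stage 2 at 50% non-response, 600 × 0.5 × 0.8/2 = 120; stage 2 at the pilot's 38%, 600 × 0.38 × 0.8/2 ≈ 91. The same formula gives the probability of a significant result:

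| Assumed gap | Stage 1 (240) | Stage 2 (120) | Stage 2 (91) |
|---|---|---|---|
| 5 points | 26-38% | 15-21% | 12-17% |
| 10 points | 72-87% | 43-58% | 34-47% |
| 20 points | over 99% | 93-98% | 84-93% |

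The lower end of each range is for 80% positivity and the upper for 90%. Positivity nearer 50% would give lower probabilities. That is possible, since only 16 of 42 pilot participants (38%) were non-responders.

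**4. First-stage contrast at week 26.** The planned model carries the first-stage indicator through all visits. With 1:1 second randomisation (assumed), the share of a frontline arm on rewards in week 25 is half its non-response rate: 0.38/2 = 19%, or 0.50/2 = 25%. Both arms contain rewarded participants, so the imbalance is diluted for this contrast.

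**5. Cost of a visit urine.** Treatment-phase urines: 2 × 24 × 600 = up to 28,800. Added: 2 × 600 = 1,200. 1,200/28,800 = 4.2%.

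**The case against.** The strongest reply is that the outcome definition itself implies a test at each visit: if point abstinence by UDS is assessed at 13 and 26 weeks, a site could fairly take a urine then. The drug screening bullet is not exhaustive, since it also omits the screening urine used for eligibility. The Table 1 entry may be a merged cell across several columns whose borders were lost in extraction. All this stands to the extent that a visit urine may well have been intended. It does not remove the gap. The running text gives the same schedule as the table, and it names Week 49 but not Weeks 13 or 26, whereas the viral load bullet names all three.

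A reader might infer that the missing values default to the last treatment-phase urine, so that the result is biased in every randomised contrast. The documents do not support this. They state no carry-forward rule and no visit window, and the only missing-data method given is multiple imputation. For the first-stage contrast at week 26 both arms contain rewarded participants. Nor can the week 12 reward be assumed to be near its maximum, because a broken streak returns it to the starting level.

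It can also be said that abstinence while rewards are live is a legitimate outcome for contingency management, and that week 49 already provides a measure after rewards end. Both are true. The plan should still say which of the two it means at weeks 13 and 26.

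**Conclusion.** The point holds as a gap in the definition of a primary outcome. Two of the three primary UDS time points have no clearly scheduled urine (week 26 none, week 13 unclear), and the plan does not name the urine that supplies them. This is more than a missing mark in a table. The nearest scheduled urines are collected under unequal reward conditions in the contrast randomised for that stage, and those of week 12 overlap the response rule.

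Whether bias arises depends on which urine is used, and its size cannot be derived from the documents. The probabilities shown rest on assumed gaps of 5 to 20 points, on reading the 80-90% base rate as UDS positivity, and on last-urine substitution. They show that the choice could matter, not that it does. Week 49 is explicitly scheduled and unaffected.

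**What to change.** - Add UDS to the Week 13 and Week 26 columns of Table 1 and to the drug screening bullet.
- Define point abstinence at weeks 13, 26 and 49 as the result of that visit urine, collected the same way for everyone and outside the reward schedule in every arm. State the visit window and how a missed sample is handled.
- Take the week 13 urine before the second-stage allocation is disclosed.
- Report the last treatment-phase urine separately, labelled as on-treatment abstinence.
- Reconcile the visit clock in Definition of effectiveness measures with the stage weeks in Randomization and Interventions and the columns of Table 1. Settle at the same time whether self-reported use is collected at week 13.

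The reward schedules themselves need not change. The cost is about 1,200 extra rapid tests (about 4%) at visits already planned, plus the wording changes. The downside is that differences at weeks 13 and 26 may look smaller than with a rewarded urine.

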The study deploys a Type-1 effectiveness-implementation hybrid design to evaluate the effectiveness of the proposed adaptive interventions and gather data on the implementation. To evaluate the effectiveness of the interventions, the study employs a Sequential Multiple Assignment Randomized Trial (SMART) design. In the first phase, participants will be randomized into two frontline interventions for 12 weeks. Based on their outcome at the end of this phase, they will be placed or randomized into three adaptive strategies for another 12 weeks (Figure 1). The economic evaluation that addresses Aim 2, aims to weigh public health and societal costs against public health and societal benefits attributed to the interventions of different intensities with a time horizon of 12 months. To address Aim 3, we will conduct an ethnographic evaluation to identify the multi-level factors that influence the adoption and scale-up of the interventions in methadone clinics. The ethnographic evaluation is guided by the Consolidated Framework for Implementation Research (CFIR). The CFIR assesses five domains of interventions, outer settings, inner settings, provider characteristics and participant characteristics. The evaluation includes pre- and post-intervention in-depth interviews with key informants who participate in the study and ethnographic observation with participants in their daily activities at the clinics and in the community settings.

Settings

[figure not shown]
Participants are recruited from the methadone clinics in Hanoi and Ho Chi Minh City (HCMC) – the two largest urban settings in Vietnam. Criteria for selecting clinics include number of patients, estimated prevalence of methamphetamine use, availability of human resources to implement study interventions, and space for intervention activities. 10 clinics in each city will be randomly selected from those that meet the criteria.

Study schedule

The study pilot phase started in November 2020. The full study implementation phase began in May 2021. To recruit 200 HIV-positive and 400 HIV-negative methamphetamine-using methadone participants from both cities, we will screen about 5,000 patients in 20 methadone clinics. A cluster

of four methadone clinics will start every six months. We expect to complete the last cluster in October 2023.

Figure 1. Study flowchart

Participants

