We will conduct activity-based costing for each intervention arm over the 20 methadone clinics. A template developed by UNAIDS is adapted to collect data on salaries for personnel and consultants, physical resources, clinical supplies and miscellaneous charges necessary to deliver each intervention type. Furthermore, any out-of-pocket or indirect costs to the participant will be collected at baseline, and at 13- and 26-week.

Definition of cost-effectiveness measures

Measures of cost-effectiveness analysis corresponded to the outcomes of interest in Aim 1 including (1) Substance use, (2) HIV risk behaviors among HIV-negative participants and HIV viral load, HIV adherence among HIV-positive participants and (3) Quality of life (Table 1). The cost-effectiveness analysis will measure the increment in cost between contrasted interventions divided by the increment in effectiveness measures.

Ethnographic evaluation

Pre-post intervention in-depth interviews

In each cluster, we will interview 12 key informants including methadone providers, clinic managers and participants under methadone treatment participating in the study. We will select at minimum 6 participants under treatment so that include old and young, employed and unemployed, and both responsive and non-responsive participants. All participants will receive VND 200 000 (~\$10 USD) for their time in each interview. Interviews will be audio-recorded and transcribed verbatim.

Ethnographic observation

This activity is composed of two elements. The first element involves ethnographers spending time with participants with their consent in intervention sessions and other daily activities in the clinic. Such observations will build a rich picture of interventions and intervention settings, including interactions between various groups (intervention providers, other staff, and participants). The second element involves the study master counselors to observe random intervention sessions and assess the fidelity of intervention delivery using a checklist.

Training and fidelity monitoring

In each selected clinic, a physician, two counselors and one nurse will participate in the study as intervention providers. The physician will ensure referral to HIV and psychiatric services when

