We will use a time-varying mixed-effects model that will be fitted to the participants' common outcome measures over time. The unadjusted model will include indicators of first-stage and second-stage intervention conditions, time of the assessment (baseline, 13-, 26-, and 49-weeks), and intervention indicators-by-time interaction terms. An additional interaction term of the two intervention indicators will be included to account for any interaction effect between the first and the second stage interventions. The adjusted model will include patients' socio-demographic characteristics, drug use history, HIV-serostatus, and location as fixed effects. The mixed-effects models will include a participant-level random effect to account for repeated observations of each participant, as well as a clinic-level random effect to account for the nested nature within the clinics. We will conduct subgroup analyses among HIV-positive and HIV-negative participants. For the HIV-positive subgroup, the specific outcomes of interest include 1) HIV viral load suppression, and 2) adherence to antiretroviral treatment; and specific outcomes for HIV-negative subgroup include 1) frequency of HIV testing and 2) HIV seroconversion. Substance use will be the common outcomes in models including participants of both HIV statuses.

To assess cost-effectiveness

We will calculate Cost Effectiveness Ratios (CER) for each of the intermediate and final outcomes. The CER is in the broadest terms the difference in per capita costs of administering one intervention (C1-C2) relative to a second, divided by the difference in outcomes between the two interventions (O1-O2):

$$CER = \frac{C1 - C2}{O1 - O2}$$

For example, calculating the CER for adding contingency management to Matrix for non-responders would yield a CER equation. In calculating the CER of high vs. low intensity contingency management at the first randomization stage, the entire range of subsequent costs will be included. Costs of delivering the interventions will be derived from clinic records of time and other inputs, as well as incentive payments, thus providing an estimate of CER from the medical system perspective. We will also evaluate CERs from a societal perspective, using a broad definition of costs, including the social costs of incarceration.

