We will conduct sensitivity analyses to estimate the extent to which the CER calculation is affected by differences in assumptions about the size of the differences in intervention effect. In particular, we will determine how sensitive the CER is to assumptions that the difference in treatment effect is one standard deviation below or above the mean estimated effect size. Similarly, we will estimate the sensitivity of conclusions to costs that are one standard deviation below or above the estimated mean.

To identify the factors influencing the adoption and scale up of the model

The qualitative analysis team will read and provide a narrative summary for each transcript. A codebook will be developed based on these summaries. Memo-writing and code-refining will be conducted throughout the analysis. Iterative analyses assess convergence of patient, provider and organizational dimensions on study measures as well as the context of the policy subsystems, cross system interactions, and resource allocation.

Analysis of non-adherence and missing data

We will first describe the extent and patterns of missingness within each variable, check for associations between missing and observed data to determine the mechanism of missingness, which could be missing completely at random, missing at random, or missing not at random. Missing data will then be handled using multiple imputation (68). Appropriate imputation techniques will be chosen for the type of missing data and the statistical tools employed (69). For sensitivity analysis, we will conduct analyses with and without multiple imputations. All participants will be analyzed on an intent-to-treat basis where the study outcomes are examined based on the random intervention assignment and not on the actual intervention received or adherence to the intervention.

Interim analyses

There is no planned interim analysis as the behavioral therapies used in this trial have no known serious adverse events and are consistently more efficacious than control conditions in treatment-seeking participants. The effect sizes of the behavioral therapies in this trial are in the

moderate range. Furthermore, any interim analysis and decision to stop the trial would likely be based on underpowered data and susceptible to error.

Oversight and Monitoring

Scientific advisory committee

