Adverse events in this trial are defined as medical issues that do not require hospitalization. Serious adverse events are defined as life-threatening events such (e.g. suicide, opioid overdose) or other events that have a negative impact on participants' life such as incarceration or compulsory drug rehabilitation. The clinic staff will communicate information about adverse events and serious adverse events to the study team right after they are informed by participants or participant families. The study coordinators in Hanoi and HCMC are responsible to report adverse events within 7 days and serious adverse events within 24 hours on REDCap with the time of onset, seriousness, duration, and outcomes. The principal investigator will decide what serious adverse events need to be reported to the Ethics Committee.

Plan for communicating important protocol amendment to relevant parties

We will first seek advice of our scientific advisory committee for all protocol amendments. Protocol amendments will undergo the review of Ethics Committee. If they are approved, we will notify the trial funder about these amendments. No protocol modifications will be implemented without ethical approval. Notification of the approved modifications will be forwarded to all study team members.

Dissemination plans

Results of this study will be published in peer-reviewed scientific articles and presented at international and regional conferences. We will organize dissemination workshops to communicate the study results to policy makers and healthcare professionals at the end of the trial. The de-identified datasets, statistical code, and full protocol are available from the first author upon reasonable request.

Ethics and Confidentiality

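### Participant costs are scheduled at baseline, 13 and 26 weeks in the text but at baseline, 26 and 49 weeks in Table 1; if the text governs, out-of-pocket and indirect costs stop at week 26 of a 12-month horizon

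*Combined protocol and SAP*

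**What the plan says.** - **Protocol, Economic evaluation (Definition of costs and data collection).** After describing activity-based costing of each arm, the text adds that "any out-of-pocket or indirect costs to the participant will be collected at baseline, and at 13- and 26-week". Week 49 is not listed.
- **Protocol, Table 1 (Assessment schedule).** There is one cost row. It names opportunity, other healthcare and social costs and is marked at baseline, week 26 and week 49. The week-13 cell is empty.
- **Protocol, Study design.** The economic evaluation compares "interventions of different intensities with a time horizon of 12 months".
- **Protocol, Definition of effectiveness measures.** "Effectiveness measures will be assessed at 13-, 26- and 49 weeks after the first week of frontline interventions". Quality of life, which is also a cost-effectiveness measure, is marked in Table 1 only at baseline and week 49.
- **Protocol, Data analysis (To assess cost-effectiveness).** For the ratio comparing high and low intensity "at the first randomization stage, the entire range of subsequent costs will be included". Two perspectives are planned. For the medical system, "Costs of delivering the interventions will be derived from clinic records of time and other inputs, as well as incentive payments". For society, "We will also evaluate CERs from a societal perspective, using a broad definition of costs, including the social costs of incarceration".
- **Same section, sensitivity analysis.** "we will estimate the sensitivity of conclusions to costs that are one standard deviation below or above the estimated mean".

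**The concern.** The two schedules share only baseline and week 26. Week 13 appears only in the text and week 49 only in Table 1. A site team could follow either and believe that it was following the protocol.

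The choice matters for the societal cost-effectiveness ratio (CER). Under the text, effects measured at week 49 would be set against out-of-pocket and indirect costs that end at week 26. Quality of life is the sharpest case, because its only follow-up value in Table 1 is at week 49. Under Table 1, costs can reach week 49, but no cost visit separates the frontline stage from the adaptive stage, and each follow-up question must reach back about half a year. The protocol states no recall period; the cost form is not in the documents and may state one.

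The planned sensitivity analysis does not help. Moving the estimated mean cost up or down by one standard deviation varies what was observed and does not supply the weeks that were not.

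**Working it through.** The plan gives no coverage figure to reproduce, so the check compares the two schedules and counts weeks.

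**Is the mismatch a table-reading artefact?** Unlikely. The cost row has the same pattern as the mental health and social support rows (baseline, 26, 49). Rows that do have a week-13 mark, such as treatment information and viral load, show all four marks. The text schedule is plain prose.

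**Inputs**
- Text schedule: weeks 0, 13, 26.
- Table 1 schedule: weeks 0, 26, 49.
- Last effectiveness visit: week 49.
- Adaptive stage: weeks 14 to 25 (Randomization and Interventions).
- Assumption A: 12 months is 52 weeks from baseline. The protocol does not define the starting point.
- Assumption B: each cost question reaches back to the previous cost visit. This gives the maximum coverage.

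**Coverage = last cost visit ÷ 52; recall = gap between successive visits**

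| Schedule | Maximum coverage | Recall (weeks) |
|---|---|---|
| Text | 26/52 = 50% | 13, 13 |
| Table 1 | 49/52 = 94% | 26, 23 |
| All four times | 49/52 = 94% | 13, 13, 23 |

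Using all four times covers no more weeks than Table 1. Its gain is a cost visit at week 13, the boundary between stages.

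**Distance between last effect and last cost under the text:** 49 − 26 = 23 weeks. This does not depend on Assumption A.

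**Range for Assumption A.** Visits are counted from the first frontline week, and two motivational sessions come before it, so baseline may be somewhat earlier. If it is *b* weeks earlier, coverage is (26 + *b*)/52 for the text and (49 + *b*)/52 for Table 1. At *b* = 52 − 49 = 3, Table 1 reaches the full horizon (52/52 = 100%) and the text reaches 29/52 = 56%. Over *b* = 0 to 3 the ranges are therefore 50–56% and 94–100%.

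**If the two places mean different items and both run**
- Opportunity, other healthcare and social costs: baseline, 26 and 49, so no late gap.
- Out-of-pocket and indirect costs: baseline, 13 and 26, so still nothing after week 26.
- Table 1 then lacks a row for the week-13 collection that the text requires.

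**Effect on the CER.** Let U be the mean participant cost per person in the unobserved weeks. True cost difference = observed cost difference + (U in high intensity − U in low intensity). The bracket is zero if U is equal in the two arms. The documents give no figure for U in either arm.

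**The case against.** **The items may be complementary.** The text speaks of out-of-pocket and indirect costs; Table 1 names opportunity, other healthcare and social costs. The text sets no schedule for social costs, and incarceration, the one societal item that the analysis section names, belongs there. For such costs the Table 1 week-49 mark stands on any reading. This narrows the gap but does not remove it: indirect and opportunity costs overlap, and out-of-pocket and indirect costs still have no week-49 collection.

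**Subsequent costs may mean stage-2 costs.** A reader might infer that the text schedule flatly breaks the promise that "at the first randomization stage, the entire range of subsequent costs will be included". The documents do not settle this. The phrase concerns the first randomisation and is followed by a sentence on delivery costs, so it can mean the adaptive-stage costs that follow from the first assignment. That stage ends at week 25, inside the week-26 visit. The promise is unmet only if it is read as running to the 12-month horizon. The horizon itself is the firmer ground.

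**Weeks are not costs.** This stands. Intervention activity ends by week 25, so the costs of attending sessions fall inside the text's window. What is lost later is of unknown size.

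**Recall.** One could argue that a short recall at week 26 under Table 1 would miss the frontline stage. That rests on a form that is not in the documents, so it is not relied on here. The fix also keeps one 23-week recall.

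**Week 13 has no questionnaire.** Partly right. Table 1 marks no self-report questionnaire at week 13, but the effectiveness section measures methamphetamine use at 13 weeks partly by self-report, so participant contact for that purpose is already planned.

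**Conclusion.** The point holds as an internal contradiction with a conditional consequence. The two participant-cost schedules differ and nothing ranks them. If the text governs, out-of-pocket and indirect costs are unobserved after week 26. That is at most 26 of 52 weeks covered, against up to 49 of 52 under Table 1, with 12 months taken as 52 weeks from baseline and full recall between visits. The 23 weeks between the last such cost visit and the last effect visit follow directly from the stated visits.

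The reach is limited to participant costs in the societal CER, within Aim 2. The effectiveness analyses and the cost side of the medical-system CER are unaffected.

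A reader might infer that the societal CER is biased. The documents do not show that: bias in the cost difference requires unobserved costs that differ by arm, and there is no information on this either way. What is established is that the planned horizon and one of the two schedules do not match.

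**What to change.** Reconcile the economic evaluation text and Table 1 to one participant-cost schedule at the existing assessment times: baseline, 13, 26 and 49 weeks. At each follow-up, ask about costs since the last visit.

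For clusters already completed, report which schedule was used, present the societal CER over the period actually observed, and label any extrapolation to 12 months as an assumption.

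**Cost.** One short added form: at week 13 if Table 1 is now followed, or at week 49 if the text is now followed. Both are existing assessment times. The change is a protocol amendment, so it needs scientific advisory committee advice first and then ethics review: "No protocol modifications will be implemented without ethical approval".

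**What it does not solve.** Recall for weeks 26 to 49 stays at 23 weeks. Under the 52-week assumption the last 3 weeks (52 − 49) stay unobserved. Completed clusters cannot regain a missed visit.
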